The study population will include Veterans 18-75 years old. They will be men or women from the greater Providence area receiving care at the VA who have been discharged from active duty, or who served in the National Guard or reserve units.

Two groups will be recruited. One group will consist of Veterans admitted to the PVAMC psychiatric inpatient unit or medical unit or identified in outpatient settings for suicide attempt or suicidal ideation with any degree of suicide plan, and/or intent to attempt suicide. This group of Veterans may be enrolled into either active or sham TMS+BCBT, if eligible. The second group will consist of DSM-V diagnosis-matched Veterans without current suicidality to act as controls. Controls will also be matched for age ± 5 years, and sex. The control Veterans, if eligible, may be enrolled in the neuroimaging and cognitive battery, and not be eligible to receive the TMS+BCBT intervention. The matching procedure is used to limit the influence disorder-specific characteristics, sex, and age-related brain/cognitive differences on group comparisons. If we are unable to meet annual recruitment goals, sex differences will be handled through statistical covariation and strata for age-matching will be broadened (± 10 years).

D2. Participant Selection:

Participants will consist of Veteran inpatients or outpatients of the Providence VAMC with active suicide ideation or related behaviors, and non-suicidal Veteran controls. The inclusion and exclusion criteria are as follows:

D2.1. Inclusion criteria:

Inclusion criteria for all participants:

- 1) Participants must be Veterans aged 18-75 discharged from active duty, National Guard, or reserves units, receiving care at the VA. They must be able to comply with all study related procedures and visits and be

capable of independently reading and understanding study materials and providing informed consent.

Inclusion criteria for Veterans with suicidal thoughts and behaviors:

- 1) Admission to a hospital or identified in outpatient settings within 2 weeks of suicidal ideation with any methods, intent and/or plans, or within 2 weeks after an attempt as

indicated on hospital chart and confirmed by administration of the Columbia Suicidal Severity Rating Scale (C-SSRS).

Inclusion criteria for non-suicidal Veterans (controls)

- 1) No evidence of current suicidality in the medical record or endorsement of current suicidal thoughts and behaviors on the C-SSRS.

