We will use the urn randomization strategy and ensure balance among treatment groups [67,68]. We have successfully used urn randomization in previous treatment studies [44, 69] and developed a computer program that conducts the randomization. Urn randomization is a biased coin randomization technique, which randomly assigns Veterans of a given subgroup to treatment conditions (i.e., active TMS+BCBT or sham TMS+BCBT) while systematically biasing randomization in favor of balance among the treatment conditions on select variables. This program enables ongoing monitoring of the effectiveness of our stratification and randomization procedures. Since the number of variables which can be successfully balanced is limited, for the current study we will include the following variables in our randomization: a) current

admission due to suicide attempt vs. suicide risk, b) number of previous suicide attempts (none, single vs. multiple), and c) gender (male vs. female).

D4.4.2 BCBT Procedures: Participants will receive a standard course of BCBT (12 weekly individual therapy sessions). These sessions will be completed in-person at the Providence VAMC. In rare circumstances (e.g., pandemic, extreme weather), these sessions may be provided via phone or video (VA approved VA Video Connect). When therapy sessions are conducted remotely, de-identified data may be collected by study staff at home due to remote

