E2.4.1 Statistical power and sample size considerations: As we view tertiary analyses as exploratory and hypothesis generating, we do not present a priori specified sample size or minimum detectable effect size statistics. We have no doubt that we may be underpowered to detect all but large moderation effects. Our inferences will be made cautiously and be guided

by confidence intervals obtained by bootstrap resampling of the observed data.

E3. Aim 2 Analytical Plan (Analyses Related to Cognition and Neuroimaging)

All de-identified data from this study for Aim 2 will be combined with data from subjects who completed neuroimaging procedures in PVAMC IRB protocol #2018-051.

E3.1 Evaluate the relationship between STBs and reward circuits involved in decision-making in Veterans.

Hypothesis: Neural and behavioral correlates of decision-making will differentiate Veterans with STBs from those without STBs.

Rationale: Suicidality is associated with maladaptive decision-making. Neuroimaging in non-Veterans has shown that STBs are accompanied by functional and anatomical differences in the striatal-to-VMPFC reward circuit implicated in decision-making. It is unknown if these potential neurocognitive markers of suicide generalize to Veterans.

Between-group contrasts of decision-making, structural MRI, and functional MRI will be used to test our hypothesis.

E5.1 Participant groups: The STB group will be comprised of Veterans hospitalized for suicide attempt (up to n=30) or suicidal ideation (up to n=30). The diagnosis matched control group is comprised of Veterans (up to n=60) without current STBs. Per power estimations computed with G Power software⁴², 85% power to detect a medium-sized effect of group (0.4) in an ANCOVA model with three groups and two covariates is afforded by a total sample size of 72, or n=24 participants per group. Our enrollment targets exceed this estimate to account for loss of participants that are unable to complete all aspects of the study.

Data sources: Decision-making tasks include the scanned reward expectancy task (card guessing), and the un-scanned Iowa Gambling and Monetary Choice (Delay Discounting) tasks. Structural MRI and diffusion MRI data. FMRI data used in Aim 1 analyses will come from either the card guessing reward task or resting state functional MRI runs.

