Rationale: Studies comparing decision-making between individuals who have made high-risk (well-organized, highly lethal) attempts vs. those making less organized or less medically serious attempts have found that decision-making is less impulsive in higher- risk attempters [86]. In fact, decision-making in high-risk attempters is even less impulsive than it is in healthy controls. Some propose that the capacity to make a serious suicide attempt develops alongside the ability to inhibit prepotent pain and fear responses associated with death [87]. Thus, paradoxically, greater inhibitory cognitive control may facilitate development of suicidal behavior. As a test of this hypothesis, we will compare behavioral and functional neuroimaging data collected during the SSRT, an inhibitory cognitive control task, between high- and lower-risk Veterans with STBs. We will also examine associations between suicide and other cognitive control measures to assess the specificity of the link between attempts and inhibitory control. to assess the specificity of the link between attempts and inhibitory control.

Participant groups: The high-risk group will be comprised of Veterans with history of suicide attempt (up to n=30), while the low-risk group will include Veterans with ideation only (up to n=30). See alternative methods for risk grouping in the Design Considerations section below. Diagnosis matched controls (up to n=60) are also used in some analyses.

Data sources: Structural data (cortical thickness and volume) and diffusion MRI data. FMRI data used in Aim 2 analyses will come from either the SSRT, the scanned decision-making task, or resting state runs. Behavioral measures of decision-making include data from the scanned decision-making task. Behavioral measures of cognitive control include data from the scanned SSRT, and the un-scanned Intra-Dimensional Card Sort and Flanker tasks.

General statistical details: Age and sex will be treated as covariates of no interest in all statistical analyses. Intracranial volume (computed by Freesurfer) will also be used as a nuisance covariate in morphometry analyses to control for size-related variance. Residual effects of motion on functional connectivity estimates will be tested post hoc by regressing individuals' frame-to- frame motion against functional connectivity beta values ⁵⁵. Potential effects of impulsivity, depression, anxiety, and sleep on outcomes will be explored in post hoc sensitivity analyses.

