Design considerations & alternative strategies for Aim 2. This design uses a categorical factor to define groups that approximates risk by history of attempt versus ideation, based on the strength of previous attempt as a risk factor for subsequent attempts. While straight-forward, we acknowledge that within-group heterogeneity may invalidate this grouping strategy. For instance, the ideation group could contain a significant number of Veterans with highly detailed suicide plans that have begun obtaining means that would be better classified as high-risk. In recognition of this issue, we will also compute empirically-determined risk categorization thresholds based on Beck Lethality Scale, Suicide Intent Scale, and Scale for Suicide Ideation scores. Alternatively, we may use continuous variables operationalizing suicidal planning, intent, or lethality for these analyses.

E3.3 (Exploratory) Integrate EHR data and neurocognitive markers into predictive models of STBs.

We will combine EHR data and objective cognitive measures forming a high-dimensional, multi-modal dataset. Machine learning algorithms will be applied to examine the predictive utility of this approach.

Rationale: Machine learning algorithms can accommodate large predictor sets and can model complex interactions among factors. Models built on EHR outperform traditional models with predictive accuracy in excess of AUC +0.70. We will subject an EHR dataset enriched with additional, objective, cognitive measures of suicidality (defined in Aims 1 & 2) to machine learning classification. Three types of supervised machine learning models (described below) will be used for this exploratory analysis. Models will be constructed both with, and without, Aim 1 & 2 measures to test if their inclusion improves suicide prediction.

Data sources: Aggregated EHR data (Section D6.2) and subject-level performance outcomes on the reward expectancy scanned task, Delay Discounting task, Iowa Gambling Task, Flanker Task, Dimensional Card Sort Task, and SSRT task.

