General approach: The dataset comprised of subject-level aggregated EHR variables and behavioral outcomes from cognitive control and reward tasks will be treated as a “discovery data set,” meaning that it will be used to train machine-learning algorithms and make initial identifications of subsets of the dataset associated with distinct suicide outcomes. Classifier training, cross-validation, and optimization will be performed using this discovery data set. The goal is to predict participants with: 1) history of attempt, 2) suicidal ideation without history of attempt, 3) no history of STBs. Future studies will attempt to replicate findings in an independent sample.

Software: Part of this exploratory aim involves testing implementations against one another. Modeling will be carried out using Julia⁶⁴, an open-source computing language, MATLAB, and R.

Machine learning algorithms:

Elastic Net Regularized Logistic Regression⁶⁵ Unlike other regularized regression methods such as ridge or lasso, elastic net models are stable when multicollinearity amongst

predictors is high. Elastic net regularization penalizes model complexity by specifically modeling overfitting simultaneously combining the shrinkage and recovery approaches of lasso and ridge regularization. This means that coefficients are all retained but undergo shrinkage toward zero. We will use a 10-fold cross-validation to assess the performance of the classifier.

Random forest machine clustering Random forest clustering is a tree-based supervised learning algorithm that can handle high multi-collinearity and is robust to overfitting [95]. Decision trees are built by recursively subsampling predictors from the training dataset [95,96]. At each “split” of a tree, the algorithm searches for a given variable and the binary decision that splits the predictor subset. As trees are built, progressively smaller predictor subsamples are drawn and used to predict earlier data splits forming “parent” and “child” nodes. The number of predictors at each node will be determined by the square root of the total number of predictors to limit over-fitting [96] and an error minimization criterion will be applied to select the predictor and cut point at each node of the decision tree that optimizes binary splits. This iterative process will continue down the tree until node size is equal to 10% of the total study sample. A 10-fold cross-validation will also be run as a preliminary validation of estimates.

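### Aim 2 groups Veterans by index event in E3.1 but by attempt history in E3.2 and E3.3, and controls are screened only for current suicidality

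*Combined protocol and SAP*

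**What the plan says.** **Entry of cases.** D2.1 admits Veterans on a recent event: "Admission to a hospital or identified in outpatient settings within 2 weeks of suicidal ideation with any methods, intent and/or plans", or within two weeks after an attempt. It sets no condition on lifetime history.

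**E3.1, participant groups.** "The STB group will be comprised of Veterans hospitalized for suicide attempt (up to n=30) or suicidal ideation (up to n=30"). The same paragraph gives the power statement: 85% power for a group effect of 0.4 in a three-group ANCOVA with two covariates, needing 72 in total or 24 per group. Targets are set higher to allow for participants who cannot complete the study.

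**E3.2, participant groups.** One group is defined by past attempts: "The high-risk group will be comprised of Veterans with history of suicide attempt (up to n=30"). The other takes the remaining cases under an equal cap: "while the low-risk group will include Veterans with ideation only (up to n=30"). The design considerations at the end of E3.2 confirm that the factor "approximates risk by history of attempt versus ideation". E3.2 has no power statement of its own.

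**E3.3, general approach.** The three classes to be predicted are history of attempt, ideation without such a history, and "3) no history of STBs".

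**Controls, D2.1.** "No evidence of current suicidality in the medical record or endorsement of current suicidal thoughts and behaviors on the C-SSRS". Nothing in the inclusion or exclusion criteria removes controls with past ideation or attempts.

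**Randomization, D4.4.1b.** The urn uses the reason for the current admission as one factor and "number of previous suicide attempts (none, single vs. multiple") as another.

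**The concern.** The reason for the current episode and lifetime attempt history are different variables, and the urn factors show that the plan knows this. Aim 2 nevertheless moves from one to the other with the same numbers attached and no rule for people on whom the two disagree.

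Two groups of people are affected. The first is Veterans identified for ideation who attempted suicide in the past. They change sides between E3.1 and E3.2, which removes people from the ideation-only group. The second is controls who are not suicidal now but once were. E3.2 compares lifetime attempters with controls in the grey-matter, inhibitory-control fMRI and decision-making analyses. As written, lifetime attempters may then be on both sides of that comparison.

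At stake are the size of the ideation-only group, a possible bias toward no difference in the control contrasts of E3.2, and the correct labelling of classes in E3.3. Without a rule fixed in advance, group assignment may also be settled after the data are seen.

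**Working it through.** **1. The plan's own figure (E3.1).** Inputs: f = 0.4, three groups, two covariates, N = 72. Two-sided alpha of 0.05 is assumed; the plan states it for the region-of-interest tests. Noncentrality = f² × N = 0.16 × 72 = 11.52, with df 2 and 72 − 3 − 2 = 67. Power is 0.853, and 72 is the smallest N that reaches 85%. The figure reproduces. The margin in each suicidal cell is 30 − 24 = 6, or 20% of 30.

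**2. Size of the ideation-only cell.** Let p be the share of 30 index ideators with a past attempt. The documents do not give p. The expected cell is 30 × (1 − p). The chance that it is below 24 is the binomial probability of 7 or more past attempters among 30.

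| p (assumed) | Expected ideation-only | Chance below 24 |
|---|---|---|
| 10% | 27 | 3% |
| 20% | 24 | 39% |
| 30% | 21 | 84% |
| 40% | 18 | 98% |

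The expected cell is below 24 only if p exceeds 20%. If attrition has already taken 30 to 24, the expected cell is 24 × (1 − p), which is below 24 at any p above zero (21.6 at 10%, 16.8 at 30%).

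**3. Illustrative power, high- v low-risk.** Assumptions: d = 0.8 (equal to f = 0.4 for two groups; the plan states no d), two covariates, no attrition. Noncentral t with noncentrality d × √(n₁n₂/(n₁+n₂)) and df n₁ + n₂ − 4.

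| p (assumed) | High-risk held at its cap of 30 | Past attempters added to high-risk |
|---|---|---|
| 0 | 30 v 30: 0.861 | 30 v 30: 0.861 |
| 20% | 30 v 24: 0.817 | 36 v 24: 0.847 |
| 40% | 30 v 18: 0.747 | 42 v 18: 0.797 |

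The right-hand column goes beyond the stated cap of 30, so the middle column is the one that follows the plan.

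**4. Controls.** Let q be the share of the 60 controls who are past attempters, also not given. If they resemble attempters fully, the contrast becomes 0.8 × (1 − q). If they are excluded instead, d stays at 0.8 and the control group becomes 60 × (1 − q). Attempters number 30; the method is that of step 3.

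| q (assumed) | Left in: d | Left in: power (30 v 60) | Excluded: power |
|---|---|---|---|
| 0 | 0.80 | 0.943 | 0.943 |
| 10% | 0.72 | 0.889 | 30 v 54: 0.935 |
| 20% | 0.64 | 0.808 | 30 v 48: 0.924 |
| 30% | 0.56 | 0.697 | 30 v 42: 0.910 |

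Full resemblance is the worst case. If these controls resemble attempters only partly, the loss is smaller. Under these assumptions, excluding them costs little.

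**5. E3.3.** No arithmetic is needed. The D2.1 criterion for controls concerns current status, whereas the E3.3 class concerns lifetime history. The first does not imply the second.

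**The case against.** **The ideation-only group will be too small.** A reader might infer that it must fall below the plan's own number. The documents do not support that. It needs p above 20%, or attrition that uses up the margin, and p is not given. The 24 comes from the three-group test in E3.1 and is only a borrowed benchmark for E3.2. A reader might also infer that 30/30 cannot be reached in E3.2. But 30 is a cap, E1 speaks of ideation and attempts without tying them to the current episode, the suicidal cells are a subsample of 130 randomised Veterans, and E3 pools Aim 2 data with another protocol of unstated size. The cells could be filled on lifetime history. What stands is that no rule says they will be.

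**E3.1 is not harmed by the split.** Its planned contrasts mostly set all suicidal Veterans against controls, where the split between attempt and ideation does not matter. That is fair, although its power statement is for three groups.

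**The plan admits heterogeneity.** The design considerations in E3.2 say that the grouping is approximate and offer thresholds or continuous measures instead. Their example is ideators with detailed plans. They do not cover past attempters among ideators or controls, and two of the scales proposed for the thresholds (Beck Lethality and Suicide Intent) are not in the Table 2 battery.

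**Controls free of current suicidality are a deliberate choice.** This is a coherent choice for E3.1. It does not suit a contrast with lifetime attempters.

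**E3.3 is mislabelled.** A reader might infer this too. E3.3 never says that controls form the third class, so a control with a past attempt could properly be placed in the first. What stands is that the assignment rule is missing.

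**Conclusion.** The conflict of definitions is in the text and depends on no assumed rate. E3.1 uses the index event, E3.2 and E3.3 use history, and controls are screened only on current status. Followed as written, E3.2 allows lifetime attempters on both sides of the attempter v control contrast.

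The numerical consequences are conditional. The ideation-only cell can fall below 24 if the cells are filled on the index event and either p exceeds 20% or attrition has taken the margin. The power figures are illustrations under assumed shares, d = 0.8 and, for controls, full resemblance to attempters. They do not show that Aim 2 is underpowered.

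The point deserves correction but is limited in reach. A5 lists the comparison of suicidal Veterans with controls as exploratory, E3.3 is itself exploratory, and the randomised comparison of active with sham TMS is untouched.

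**What to change.** 1. Define attempt history once, on a lifetime basis, from data already planned at baseline: the C-SSRS interview (Table 2), the previous-attempt count used in the urn (randomised Veterans only) and the chart extraction of current and lifetime suicidality (Table 5). The documents do not list the C-SSRS items given, so confirm that they cover lifetime attempts, for controls as well.
2. Use that definition to fill the scanned cells of up to 30 and 30, and to group participants throughout E3.1 to E3.3.
3. Exclude controls with a lifetime attempt from the E3.2 control contrasts, with a sensitivity analysis that includes them.
4. In E3.3, assign every participant, controls included, to a class by lifetime history and not by recruitment arm.
5. Reconcile the word hospitalized in E3.1 with D2.1, which also admits Veterans identified as outpatients.

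**Cost.** Mainly protocol wording. The ideation-only cell fills more slowly: to reach 30, about 38 index ideators are needed at p = 20% (30/0.8 = 37.5) and 50 at p = 40% (30/0.6). E3.2 has fewer controls (48 of 60 at q = 20%), and some matched pairs are lost.

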- 2) Matched to a participant with suicidal thoughts and/or behaviors on DSM-V diagnosis, age \pm 5 years, and sex.

Exclusion criteria:

Exclusion criteria for all participants:

- 1) Primary psychotic disorder (e.g. schizophrenia, schizoaffective disorder)
- 2) Cognitive impairment (as indicated by neuropsychological evaluations and/or diagnoses related to cognitive impairment [e.g., dementia] in the chart)
- 3) Pregnancy/lactation, planning to become pregnant during the study, childbearing potential and does not agree to consistent use of a measure of birth control during the scanning and TMS portions of the study. Confirmation of non-pregnancy among hospitalized patients will be obtained from the medical record review as pregnancy tests are required for psychiatric hospitalization. Pregnancy tests will be administered prior to MRI scanning and/or TMS for control participants or suicidal participants identified outpatient.
- 4) Lifetime history of moderate-to-severe traumatic brain injury.
- 5) Current unstable medical condition.
- 6) Current (or past, if appropriate) significant neurological disorder.
- 7) Lifetime history of: seizures, CNS tumors, stroke, cerebral aneurysm.
- 8) Active moderate-to-severe substance use disorder (within last month, excluding nicotine/caffeine dependencies).

Exclusion criteria specific to TMS+BCBT:

- 1) For safety, participants must meet established screening criteria following MRI safety. MRI involves magnetic fields at similar intensity to those emitted from the TMS stimulation coil. Unless devices are MRI-safe patients may not have:
 - a. Cardiac pacemaker, implanted device (deep brain stimulation) or metal in the brain, cervical spinal cord, or upper thoracic spinal cord
- 2) Other exclusions include conditions that could be worsened by TMS, such:
 - b. Bipolar I disorder or an increased risk of seizures in the case of severe and uncontrolled substance use disorder
- 3) Patients who have previously received Theta Burst Stimulation cannot be enrolled in this study
 - a) The risk of the patient recognizing the difference between active versus the sham would jeopardize the double-blinding framework proposed in this protocol as well as the credibility of reported data.

Exclusion criteria specific to Neuroimaging:

- 1) MRI contraindications (e.g., cardiac pacemaker, non-MRI safe implants, shrapnel, permanent makeup).

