this naturalistic sample will be more representative of Veterans with STBs. Heterogeneity however, may beget misclassification errors i.e. classification by disorder versus suicidal outcome. The AUC statistic is our planned metric for model comparisons because it easily interpreted. However, AUC metrics can overestimate true performance when applied to a larger dataset where one group is comparatively over-represented i.e. a high AUC is achieved by algorithms optimizing the identification of controls over cases. Alternative performance measures that simultaneously evaluate positive predictive value and sensitivity like precision- recall statistics may be a more robust alternative to AUC.

E3.4.2 Volume-space structural preprocessing. T1-weighted images will undergo intensity normalization, tissue segmentation, and volume-space registration to the Montreal Neurological Institute (MNI)-152 Atlas.

E3.4.3 Surface-space structural preprocessing. T1-weighted images will be resampled to Freesurfer-conformed space, then submitted to intensity normalization, tissue segmentation, spherical registration, volume-space registration to the MNI-152 Atlas. Freesurfer preprocessing also includes surface-space cortical parcellation and volume-space subcortical parcellation.

E3.4.4 General fMRI preprocessing. The following preprocessing steps apply to all fMRI data. Steps include slice-time correction, head motion estimation, realignment, inhomogeneity correction via field map, functional segmentation, registration to MNI-152 space, and an artifact analysis in which high motion volumes (>0.5mm translational or 0.02 rotational motion), or volumes where global signal variance exceeds 3 standard deviations are flagged for nuisance regression in subsequent models. Spatial smoothing with a 4mm full-width, half max Gaussian kernel will be applied to fMRI data subjected to univariate analyses to improve conformation to the assumptions of Random Field Theory.

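### E3.2: the attempt-versus-ideation contrast is neither matched on nor adjusted for psychiatric diagnosis, so a disorder difference could create or mask an apparent marker of risk severity

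*Combined protocol and SAP*

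**What the plan says.** **Groups.** E3.2 defines them by history: "The high-risk group will be comprised of Veterans with history of suicide attempt (up to n=30"). The comparison group, of the same maximum size, has ideation without an attempt. Matched controls enter only some of the E3.2 analyses. The white-matter models contrast high-risk with low-risk Veterans directly.

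**Adjustment.** Under general statistical details, E3.2 states: "Age and sex will be treated as covariates of no interest in all statistical analyses". For morphometry, "Intracranial volume (computed by Freesurfer) will also be used as a nuisance covariate in morphometry analyses to control for size-related variance". Beyond that, "Potential effects of impulsivity, depression, anxiety, and sleep on outcomes will be explored in post hoc sensitivity analyses". The decision-making models list group, inhibitory control, impulsivity or fMRI activation as predictors. Diagnosis appears in none of these lists.

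**Matching.** D1 gives its purpose: "The matching procedure is used to limit the influence disorder-specific characteristics, sex, and age-related brain/cognitive differences on group comparisons". The control inclusion criterion in D2.1 shows who is matched to whom: "Matched to a participant with suicidal thoughts and/or behaviors on DSM-V diagnosis", and also on age and sex. D3.1.2 and E1 describe the same control-to-patient matching.

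**Awareness of the problem.** The E3.3 design considerations call the sample transdiagnostic and warn of "classification by disorder versus suicidal outcome", but only for the machine-learning models. The E3.2 design considerations discuss misclassified risk level, not diagnosis.

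**Data available.** Table 2 schedules the SCID-V and a borderline personality screen (MSBPD) at baseline.

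**The concern.** The plan treats three factors as able to distort brain and cognitive comparisons: diagnosis, sex and age. For suicidal Veterans versus controls, all three are handled by matching. For attempters versus ideators there is no matching, and the models carry over only age and sex.

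The diagnostic range is wide. D2.2 says borderline personality disorder is not exclusionary here; in the study on which recruitment was modelled, it accounted for 35 of 168 people screened (21%).

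E3.2 interprets attempt-versus-ideation differences as indicating risk severity, and asks whether the link with attempts is specific to inhibitory control. If a disorder that affects inhibitory control, impulsive choice or prefrontal measures is commoner in one group, the contrast mixes disorder with risk.

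The distortion can go either way. E3.2 expects higher-risk Veterans to be less impulsive and to have superior control regions. An excess among attempters of a disorder that impairs control would hide that effect; a deficit of such a disorder would imitate it.

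**Working it through.** **1. The plan's own figure.** E3.1 has the only imaging power statement: 85% power, effect size 0.4, three groups, two covariates, total 72. Alpha is not given with it; 0.05 is assumed. Noncentral F with λ = N·f² = 72 × 0.16 = 11.52 and df 2 and 72 − 3 − 2 = 67 gives power 0.853. The figure reproduces, and two covariates is consistent with age and sex alone.

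**2. Does matching balance attempters against ideators?** Each control is matched to one suicidal Veteran, so the controls mirror the pooled suicidal group. Adding them as a third group leaves any diagnosis gap between its two halves untouched.

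**3. Size of the bias (assumed inputs).** Let a binary diagnosis, centred on 50% prevalence, differ systematically by D between the groups and shift the outcome by δ within-diagnosis SD. With no true group effect, the expected spurious difference is D × δ. Type I error was simulated for 30 v 30 in a linear model with group, age and sex, at two-sided 5%, with 8,000 runs per cell. Entries are bias in SD, then rejection rate.

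| D | δ = 0.3 | δ = 0.5 | δ = 0.8 |
|---|---|---|---|
| 0.1 | 0.03; 5.2% | 0.05; 5.0% | 0.08; 5.3% |
| 0.2 | 0.06; 5.5% | 0.10; 6.5% | 0.16; 8.7% |
| 0.3 | 0.09; 6.6% | 0.15; 8.6% | 0.24; 13.6% |
| 0.4 | 0.12; 7.5% | 0.20; 10.9% | 0.32; 21.1% |

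With diagnosis as a covariate (run at δ = 0.8), rejection was 4.6% to 5.6%.

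**4. Chance imbalance.** With no systematic association and 50% prevalence, the prevalence difference has SD √(2 × 0.5 × 0.5/30) = 0.129, and a gap of 20 points or more occurs with probability 0.155. The unadjusted test still rejected in 4.9% to 5.0% of runs at D = 0. Chance imbalance is already part of the residual variance and does not inflate the error rate.

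**5. Region-of-interest tests.** E3.2 Bonferroni-corrects these. The number of comparisons is not stated. Assuming seven, the nominal level per test is 0.05/7 = 0.7%. A noncentral t calculation (df 56) gives 1.1% at a bias of 0.10 SD and 6.8% at 0.32 SD. It treats the bias as fixed and ignores the variance that diagnosis adds, so it slightly overstates the top end (23.0% against the simulated 21.1% at the 5% level). The absolute rates fall; the relative inflation remains.

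**6. Cost of adjusting.** In the plan's three-group calculation, one to four extra covariate terms move power at N = 72 from 0.853 to 0.852, ignoring collinearity. For 30 v 30, the minimum detectable d at 80% power is 0.74 with age and sex. Under step 3 the squared correlation of group and diagnosis is D², so the variance inflation is 1/(1 − D²) and d is multiplied by its square root:

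- D = 0.2: inflation 1.04, d about 0.75
- D = 0.3: inflation 1.10, d about 0.77
- D = 0.4: inflation 1.19, d about 0.80

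**The case against.** **The confounding is partly handled.** Impulsivity, depression and anxiety are examined post hoc, and impulsivity is a predictor in the decision-making models. Primary psychotic disorder and active moderate-to-severe substance use disorder are excluded for everyone, and Bipolar I for the intervention. This narrows the diagnostic range but does not balance it. Symptom scores are not diagnoses, and PTSD and personality disorder remain uncovered.

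**The mixed sample is deliberate.** It was chosen as more representative, and disorder may be part of what separates attempters from ideators. A diagnosis-adjusted contrast then answers a narrower question. This stands, and is a good reason to report both results rather than replace one with the other.

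**The stakes are limited.** A5 labels the brain-behavior hypotheses exploratory, and the randomized treatment comparison does not depend on this contrast. That stands too, although E3.2 does describe its region-of-interest tests as primary hypothesis testing.

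**Stronger readings to avoid.** A reader might infer that the contrast will be confounded. The documents give no diagnosis distribution by risk group and no diagnosis effect, and at a 10 point difference the inflation is negligible. A reader might cite likely chance imbalance at 30 per group as evidence of inflated error; step 4 shows it is not. A reader might extend the point to E3.1, where the same covariate sentence appears, but there the diagnosis matching already covers suicidal Veterans versus controls.

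**Conclusion.** The gap is real and specific to the E3.2 high-risk versus low-risk contrast: no section matches these groups on diagnosis and no E3.2 model adjusts for it, although the plan treats diagnosis as a source of distortion elsewhere and collects it at baseline.

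The consequence is conditional. It needs a systematic association between diagnosis and attempt history, together with a diagnosis effect on the measure. Over the assumed range the error rate runs from essentially nominal to about four times nominal per uncorrected test. Those rates describe tests such as the behavioral group comparisons, for which E3.2 states no multiplicity correction. The direction cannot be settled from the documents. This is worth correcting before analysis, but it does not threaten the trial's treatment comparison.

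**What to change.** For the E3.2 high-risk versus low-risk models only:

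- Prespecify a diagnosis-adjusted analysis with grouped primary SCID-V diagnosis (for example mood, trauma-related, other) as a covariate, reported beside the age- and sex-adjusted result.
- Add the MSBPD score as a further sensitivity covariate, since one primary-diagnosis factor does not capture comorbid personality pathology.
- Tabulate diagnosis by attempt and ideation group.
- State that a difference will be called a marker of risk severity only if it persists after adjustment.

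No change is needed to the E3.1 comparison of suicidal Veterans with controls.

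The cost is a change of wording in the analysis plan, using variables already in the baseline battery. It spends a few degrees of freedom and brings some collinearity between group and diagnosis, with the loss of precision shown in step 6. The adjusted result must be described as a within-diagnosis contrast.
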